### 6.2. Analysis Population

The analysis population will consist of all enrolled patients who received the study treatment.

### 6.3. Study Patients

### 6.3.1. Patient Demographics

Summary statistics of the patient demographics including age, sex, race, ethnicity and baseline characteristics will be presented by cohort. Additionally, a listing table will be provided.

#### 6.3.2. Patient Disposition

An accounting of study patient disposition, including total number of patients enrolled, early study drug discontinuations, early withdrawal from study, and summary of reasons for study drug discontinuation and study withdrawal, will be presented by cohort. Also, a listing with the reasons for early study drug discontinuations and study withdrawals study withdrawals will be provided.

#### 6.4. Concomitant Therapy

Concomitant medications will be coded using the WHO Drug Dictionary. Prior medications that are ongoing at the time of study enrollment will also be recorded. A listing table of all concomitant medications will be provided.

#### 6.5. Pharmacokinetic Analysis of Betrixaban

#### 6.5.1. **Primary PK Parameters**

The primary PK Parameters are as follows and will be presented per age group by dose, and for individuals, where possible:

- Area under the concentration-time curve to the last measurable concentration above the quantitation limit (AUC(0-last))
- Maximum observed plasma concentration (Cmax)

Summary statistics and listing tables of  $C_{max}$  and AUC will be provided for each age and dose cohort. The subjects who only had 5 time points each will have PK parameters calculated as an average, as it would not be appropriate to assume Cmax or calculate AUC based on the limited time points.

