- \circ ln(2)/(- β), where β is the slope of the terminal portion of the log concentration–time curve.
- Time to maximum observed plasma concentration (T_{max}).
- Maximum observed plasma concentration (C_{max}).
- Area under the plasma concentration-time curve from 0 to last available measurable concentration (AUC_(0-last)) computed using the linear trapezoidal rule.
- Clearance (CL/F), calculated by dividing the administered dose by the AUC_(0-∞).
- Volume of Distribution (Vd/F), calculated by dividing the dose administered by the plasma concentration at the first time point measured.
- Total area under the plasma concentration-time curve from time 0 to infinity (total AUC), computed as:
 - Total AUC $(AUC_{(0-\infty)}) = AUC_{(0-last)} + CP_{last} / (-\beta)$ where $AUC_{(0-last)}$ is the area under the curve from time 0 to the time point of the last measurable concentration above the quantitation limit; CP_{last} is the last

measurable concentration above the quantitation limit; and ß as defined as above.

Pharmacodynamic Assessment:

The following PD assessment will be determined at a sub-set of timepoints collected for PK analysis. Data may be normalized to pre-dose samples and expressed as % of pre-treatment or the values measured may be used.

- Anti-FXa activity
- TF-initiated thrombin generation assay in platelet poor plasma.

Safety:

Safety and tolerability will be determined by change from baseline in symptoms, signs, and laboratory tests, by elicitation of treatment emergent AE (TEAEs), and by concomitant medication usage. All AE events will be followed until resolution and appropriately reported on the AE Case Report Form. Laboratory abnormalities will be reported as AEs if deemed to be clinically significant per the Principal Investigator.

Statistical Methods:

Primary PK parameters, $AUC_{(0-last)}$, and C_{max} will be determined for each patient using plasma level of betrixaban assessed at baseline, during the first 24 hours, and 120 hours post dosing. Other PK parameters, Total AUC $(AUC_{(0-\infty)}) t_{1/2}$, T_{max} , CL, and V_d/F will also be determined, data permitting. Descriptive statistics such as geometric mean and 90% CI for PK parameters will be summarized by gender for each age group.

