8.0 PHARMACOLOGICAL ASSESSMENTS

8.1. Pharmacokinetic Assessments

The plasma portion of the blood samples will be assayed for determining the PK parameters of betrixaban. The following PK parameters will be calculated for each age groups using POP PK methodology as long as sufficient data is available:

- Terminal plasma half-life ($t_{\frac{1}{2}}$), determined by linear regression of the log concentration on the terminal portion of the plasma concentration–time curve. Half-life is calculated as $ln(2)/(-\beta)$, where β is the slope of the terminal portion of the log concentration–time curve.
- Time to maximum observed plasma concentration (T_{max}).
- Maximum observed plasma concentration (C_{max}).
- Area under the plasma concentration-time curve from 0 to last available measurable concentration (AUC_(0-last)) computed using the linear trapezoidal rule.
- Clearance (CL/F), calculated by dividing the administered dose by the AUC_(0-∞).
- Volume of Distribution (V_d/F) , calculated by dividing the dose administered by the plasma concentration at the first time point measured.
- Total area under the plasma concentration-time curve from time 0 to infinity (total AUC), computed as:
 - Total AUC $(AUC_{(0-\infty)}) = AUC_{(0-last)} + Cp_{last} / (-\beta)$ where $AUC_{(0-last)}$ is the area under the curve from time 0 to the time point of the last measurable concentration above the quantitation limit; Cp_{last} is the last measurable concentration above the quantitation limit; and β as defined above.

8.1.1. Blood Sample Collection

Blood samples for PK analysis will be collected using 3.2% Na Citrate as the anticoagulant. Blood samples for PK assessments will be collected 30 minutes prior to the dose administration, and at 0.5, 1, 2, 3, 4, 6, 12, 24, and 120 hours post dose with the 6 hour time point only being collected in the patients with rich PK sampling. Blood samples for patients in the POP PK analysis groups will be taken at time points based on the sequences to which each patient is assigned.

8.1.2. Urine Sample Collection

Urine samples will not be collected for centralized testing.

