10.4. Determination of Sample Size

Sample size for each age group is determined by the variance for $AUC_{(0-last)}$ and C_{max} observed from the adult PK studies of betrixaban. The between-subject variability seen in $AUC_{(0-last)}$ as measured by percent coefficient of variation was around 45%. A minimum of 12 subjects are required to target a 90% confidence interval within 60% and 140% of the geometric mean estimates of the $AUC_{(0-last)}$ with at least 80% power.

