10.6.2. Other PK Parameters

- t_{1/2}
- T_{max}
- CL/F and V_d/F

Summary statistics for the PK parameters will be tabulated by gender for each age group.

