After dosing, patients will undergo serial blood sampling for PK-PD evaluations (the Schedule of Assessments detailing all procedures is provided in Table 5). The PK and PD data from Part 1 will be used for dose determination for the next youngest age group using POP PK and PBPK modeling and simulation. The primary PK parameters to be determined are  $AUC_{(0-last)}$  and  $C_{max}$ . Other PK parameters to be determined are Total AUC ( $AUC_{(0-\infty)}$ ),  $t_{1/2}$ ,  $T_{max}$ , CL/F, and  $V_d/F$ . These will be estimated using POP PK methodology for age groups except the initial group of patients for which rich PK sampling is done.

Following analysis of Part 1 data and an amendment to the protocol, a Part 2 of the study was originally planned to commence. However, since Portola decided not to continue to develop the betrixaban program, Part 2 of this study will no longer be performed.

For both of the cohorts in Part 1, safety assessments (evaluation of AEs, concomitant medications, routine chemistries [hematology, coagulation, serum chemistries]) will occur at protocol-specified time points.

The schema of the original study design is depicted in Figure 1. Note that Part 2 will not be performed.

Study Part	Part 1	Part 1	Part 2 - TBD Amendment
Cohort No.	Cohort 1	Cohort 2	Cohort 3
Age	12 to < 18 years	12 to < 18 years	2 to $<$ 12 years
Dose	40 mg	80 mg	TBD
n =	3 patients (one of each gender)	18 patients (at least two of each gender)	12 patients (at least two of each gender)
PK Sampling	Rich - 10 time points	Sparse - 5 time points	Sparse – TBD time points
PK Time Points	Pre-dose, 0.5, 1, 2, 3, 4, 6, 12, 24, 120 hours	Sequence A: pre-dose, 1, 3, 12, 120 hours Sequence B: pre-dose, 0.5, 2, 4, 24 hours Sequence C: pre-dose, 2, 3, 12, 24 hours	Sequence D: TBD Sequence E: TBD

Figure 1: Schema of Study 16-021

A detailed Schedule of Activities can be found in Protocol, Appendix A.

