## 4.0 EFFICACY AND SAFETY VARIABLES

#### 4.1. Pharmacokinetic Parameters

Plasma levels will be assessed at baseline, during the first 24 hours, and 120 hours post dosing and will be used to estimate betrixaban population PK parameters shown below for each age and dose group based on average profiles or individual profiles if available:

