## 6.0 STATISTICAL METHODS

### 6.1. General Considerations

After final database lock, all analyses will be performed according to this Statistical Analysis Plan (SAP).

All parameters will be summarized descriptively. No hypothesis tests will be performed. For continuous variables, number of observations, mean, median, standard deviation, and minimum and maximum values, and 95% CI will be presented. For categorical variables, counts, percentages, and 95% CI will be tabulated for each category.

It is anticipated that statistical summaries will be performed using SAS Version 9.4 (SAS Institute, Inc., Cary, NC, USA) or higher. Additional software may be used for the production of graphics and for statistical methodology not available in SAS.

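### The SAP's default summary (mean, SD, 95% CI) does not fit AUC(0-last) and Cmax: it leaves the 80 mg cohort with no defined interval, and SAP 6.11 does not record the departure from the protocol

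*SAP*

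**What the plan says.** **SAP.** Section 6.1 covers all parameters. For continuous variables, "number of observations, mean, median, standard deviation, and minimum and maximum values, and 95% CI will be presented". It makes no exception for PK. Section 6.5.1 promises unspecified summary statistics and listings of Cmax and AUC for each age and dose cohort. It then adds, for the sparsely sampled patients: "The subjects who only had 5 time points each will have PK parameters calculated as an average". The reason it gives is that individual values from so few samples would not be appropriate.

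On method, SAP 4.1 has the parameters estimated "for each age and dose group based on average profiles or individual profiles if available". SAP 3.1 says "These will be estimated using POP PK methodology for age groups except the initial group of patients for which rich PK sampling is done". No part of SAP section 6 describes a POP PK analysis. Section 6.5.2 cancels the other PK parameters. Section 6.11 lists two changes only: Part 2 was not conducted, and the PD measures were not taken.

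**Protocol.** The synopsis states: "Descriptive statistics such as geometric mean and 90% CI for PK parameters will be summarized by gender for each age group". Section 10.6.2 repeats the by-gender part: "Summary statistics for the PK parameters will be tabulated by gender for each age group". Section 10.4 sizes each age group on the same kind of interval: "A minimum of 12 subjects are required to target a 90% confidence interval within 60% and 140% of the geometric mean estimates", with a CV of about 45% and at least 80% power. Section 8.1 has AUC(0-last) "computed using the linear trapezoidal rule".

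**The concern.** AUC(0-last) and Cmax carry the primary objective and are the only PK results left. Followed literally, the SAP gives the 80 mg cohort a point value with no stated uncertainty. It gives the 40 mg cohort an interval that can include negative exposure. Neither result lines up with the quantity on which the protocol based its precision.

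The analyst would also have to choose the averaging scale, the variance method and even the type of analysis after seeing the data, because three SAP sections point to different approaches. A reader of the study report who consulted SAP 6.11 would not learn that the summary had moved away from the protocol.

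**Working it through.** **Inputs.** From the documents: CV 45%, limits 60% and 140%, N = 12 (protocol 10.4); Cohort 1 n = 3; Cohort 2 n = 18, six in each of sequences A, B and C (SAP 3.1 and Figure 1); peak at 3 to 4 h (protocol 1.0). SAP 6.1's mean is read as arithmetic.

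**1. The protocol's N.** Log-scale SD: σ = √ln(1 + 0.45²) = 0.4294. Success means that the whole interval m ± t·s/√n lies between ln 0.6 = -0.511 and ln 1.4 = 0.336 around the true log mean. By simulation, with a 90% CI:
- n = 11: about 76%
- n = 12: about 80%

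So N = 12 reproduces for a geometric mean with a log-scale 90% CI.

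**2. Effect of the 95% level alone** (one AUC per patient).

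| n | 90% CI | 95% CI |
|---|---|---|
| 12 | 80.2% | 65.9% |
| 18 | 93.8% | 87.7% |

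**3. Cohort 1, n = 3, observed CV 45%.**
- Arithmetic 95% CI: 1 ± 4.303 × 0.45/√3 = -0.118 to 2.118 times the mean.
- The lower limit is negative whenever the observed CV exceeds √3/4.303 = 40%. This happens in about 39% of simulated lognormal samples of three.
- Log-scale 90% CI: exp(± 2.920 × 0.4294/√3) = 0.485 to 2.063 times the geometric mean. It is wide too, but cannot be negative.

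**4. Cohort 2.** Planned samples per nominal time: predose 18; 0.5 h 6; 1 h 6; 2 h 12; 3 h 12; 4 h 6; 12 h 12; 24 h 12; 120 h 6. Different patients supply different times, so an average profile yields one AUC and one Cmax. With one value, the SD and the t-based CI of SAP 6.1 are undefined (0 degrees of freedom).

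**5. What a mean-profile AUC would estimate.** Between 24 and 120 h the linear rule draws a single segment of 96 h, resting at its far end on the six sequence A patients. If decline is exponential with rate k = ln 2/half-life, that segment contributes 96 × (C24 + C120)/2, while the true area is (C24 - C120)/k.

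| Assumed half-life | C120/C24 | Trapezoid (× C24) | True (× C24) | Ratio |
|---|---|---|---|---|
| 10 h | 0.0013 | 48.1 | 14.4 | 3.3 |
| 20 h | 0.036 | 49.7 | 27.8 | 1.8 |
| 40 h | 0.189 | 57.1 | 46.8 | 1.2 |

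The full profile was modelled as one-compartment oral with the peak at 3.5 h. The segment is 46% (10 h) to 67% (40 h) of the typical trapezoid AUC, which exceeds the true AUC(0-120) by 50% and 14% respectively. Between-patient variation was then added: F CV 20% or 40%, CL CV set so that CL/F has CV 45%, V CV 30%, ka CV 50%. The mean-profile AUC is then about 22-60% above the geometric mean of the true AUC(0-120). It is only 5-10% above a geometric mean of trapezoid AUCs taken on the same sparse times.

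Half-life and the variance split are assumptions, not in the documents. No quantitation limit was modelled. If the 120 h values fall below it, AUC(0-last) ends earlier and this segment drops out.

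**6. By gender.** Cohort 1 has three patients with at least one of each sex, so one sex has a single patient and no SD. Cohort 2 guarantees only two of each gender, and two patients cover at most two of the three sequences.

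**The case against.** - **The protocol is not strict.** The synopsis introduces the geometric mean and 90% CI only as an example, protocol 10.6.2 says only summary statistics, and protocol 10.3 leaves full definitions to the SAP. This stands as to how binding the synopsis is. It does not explain why the SAP moved off the sizing metric of protocol 10.4 without saying so.
- **An interval for Cohort 2 is possible.** A reader might infer that none can be computed. That goes too far: POP PK, a bootstrap over patients or a batch-design variance would each give one. Only the SAP 6.1 default fails. The defect is that the SAP names no alternative.
- **Averaging is not new.** The protocol synopsis already allows average profiles, and SAP 6.5.1 gives its reason openly. Agreed; averaging as such is not criticised.
- **The POP PK sentence in SAP 3.1 may concern only the other parameters**, which it directly follows and which SAP 6.5.2 cancels. That reading is possible, but it leaves the Cohort 2 method still thinner.
- **The move to 95% defeats the 60-140% target.** A reader might infer this from the n = 12 figures. At the planned 18, with one AUC per patient, containment is still about 88%. Sparse sampling, which is the protocol's own choice, is what removes per-patient AUCs.
- **Little is at stake.** Development has stopped, Part 2 is cancelled and nothing is tested. In Cohort 1, listings, median and range are planned, and neither interval is informative at n = 3. This limits the severity but does not supply the missing interval for the primary result at 80 mg.

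**Conclusion.** The point holds and should be fixed; it does not threaten the study. SAP 6.1's default does not suit the primary PK parameters. In Cohort 1 it can give a negative lower limit (about 39% of samples at CV 45%, lognormal data). In Cohort 2, 18 of 21 planned patients, it has no per-patient values to work on and nothing replaces it. The departures in statistic, CI level and by-gender summary are unrecorded. There is no type I error issue.

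Confidence is high for the reading of the documents and for the n = 3, 12 and 18 figures. It is lower for the sparse-design sizes (46-67% and 22-60%), which depend on the assumed half-lives and variances. One might also be tempted to treat a mean-profile AUC with a well-behaved interval as a near substitute for the geometric mean AUC. The documents do not support that: such an interval is precise only around the trapezoid AUC on the sampled times, which can sit well above the true AUC.

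**What to change.** 1. **SAP 6.1 and 6.5.1.** Where individual values exist, report the geometric mean and a log-scale 90% CI for AUC(0-last) and Cmax, by dose cohort. Label the Cohort 1 interval descriptive and show it beside the planned listings.
2. **SAP 6.5.1, Cohort 2.** Name one method with its interval. Either:
   - the POP PK approach of SAP 3.1; or
   - the AUC of the mean profile, with a 90% CI from a batch-design variance (within-sequence variance summed over A, B and C) or a patient-level bootstrap. State the averaging scale and how values below the quantitation limit enter the mean.

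   If the mean profile is used, label it as such and not as a geometric mean. Say that the CI covers only the trapezoid AUC on the sampled times, and warn that the 24-120 h segment can dominate and inflate it. Add AUC(0-24), or a log-linear rule on the declining segment, as a sensitivity analysis. Report the composite Cmax as descriptive only: it is the peak of the mean profile, not a mean of individual peaks.
3. **SAP 3.1, 4.1, 6.5.1 and 6.11.** Reconcile the first three on method. Record in 6.11 the changes of statistic, CI level and method, and the by-gender PK summary if it is dropped or reduced to listings.

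Cost: SAP wording and modest analysis work. POP PK needs modelling effort; the mean-profile route needs little but does not estimate a geometric mean. No extra patients or samples.

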Under Protocol 16-021, pediatric patients who meet study entry criteria will receive an open-label, single dose of orally administered betrixaban. The following age categories will be tested: 12 to < 18 years, and 2 to < 12 years. Part 1 will enroll 21 adolescents 12 to < 18 years of age, grouped in to 2 cohorts; each cohort will be dosed sequentially. The first cohort (3 patients) will receive betrixaban at 40 mg in the fed state, and have rich PK sampling consisting of 10 sampling time points. The second cohort (18 patients) will receive betrixaban at 80 mg in the fed state, and undergo one of three sequences of sparse PK sampling consisting of 5 sampling time points per sequence. Based on the results obtained in Part 1, the protocol will be amended and Part 2 will enroll 12 patients 2 to < 12 years of age who will receive a single oral dose of betrixaban based on weight as predicted by the results of the PK modeling and safety in the adolescents. An oral pediatric formulation is being developed in parallel with Part 1 of this study so that weight-based dosing of smaller pediatric patients will be possible. Part 2 PK sampling sequences will be determined following analysis of Part 1 data.

Data collected from this initial PK study in adolescents will be used to confirm both the POP PK and PBPK models, the appropriateness of weight-based dosing in adolescents, and recommend the weight-based dosing levels in children 2 to < 12 years of ageand adolescents who are below the weight range for the dose of the capsule determined to be appropriate for adolescents based on the PK study.

This trial will be conducted subject to the permission of a local Ethical Review Board, according to the Declaration of Helsinki, according to Good Clinical Practice and local regulatory requirements, and in compliance with this protocol.

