10.5. Analysis Populations

The evaluable PK population will include all individual patients who receive study drug and have sufficient blood samples through Day 1 to compute either C_{max} or total AUC assessments. For the POP PK analysis all samples from all patients will be included in the POP PK analysis.

The Safety population will include all patients who receive any amount of study drug.

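### SAP 6.5.1 gives Cohort 2's primary PK parameters as an undefined average where SAP 3.1 and the protocol say POP PK; the change is undeclared, and a pooled profile cannot supply the required SD, range and CI

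*SAP*

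**What the plan says.** Protocol 3.1 and SAP 3.1 describe the same method for the PK parameters. In SAP 3.1: "These will be estimated using POP PK methodology for age groups except the initial group of patients for which rich PK sampling is done". Protocol 8.1 and 10.6 also name POP PK for each age group, with individual estimation only for richly sampled patients. Protocol 10.5 adds: "For the POP PK analysis all samples from all patients will be included in the POP PK analysis".

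SAP 6.5.1 then states for Cohort 2: "The subjects who only had 5 time points each will have PK parameters calculated as an average". Its reason is that five time points are too few to take a Cmax or compute an AUC for an individual. It does not say what is averaged, on which scale, or how uncertainty is obtained. No model appears anywhere in SAP section 6. SAP 6.11 lists two changes only: Part 2 was not conducted and PD was not measured.

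The protocol synopsis and SAP 4.1 use a third formulation, population parameters based on average profiles or, where available, individual ones. The Introduction gives the purpose of the adolescent data: they "will be used to confirm both the POP PK and PBPK models, the appropriateness of weight-based dosing in adolescents".

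**The concern.** AUC(0-last) and Cmax are the primary parameters, and Cohort 2 is 18 of the 21 Part 1 patients. Two analysts following SAP 3.1 and SAP 6.5.1 would produce different primary results, and nothing says which governs.

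The stated reason for averaging is an argument against computing individual non-compartmental values from five samples. It is not an argument against POP PK, which exists to combine sparse samples across patients. Averaging by time point also ignores that each patient contributes four linked post-dose samples, and it discards body weight. At stake are whether the promised summaries can be produced at all, how precise and unbiased Cmax is, and whether Part 1 says anything about weight.

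**Working it through.** **1. The plan's own precision figure.** Inputs from Protocol 10.4: variability "as measured by percent coefficient of variation was around 45"%; "A minimum of 12 subjects are required"; "required to target a 90% confidence interval within 60% and 140% of the geometric mean estimates"; "with at least 80% power".

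Log-scale SD = √ln(1 + 0.45²) = 0.429. Power is the probability that the whole 90% t-interval lies between ln 0.6 and ln 1.4 around the true geometric mean. Simulation gives 76.0% at n = 11 and 80.3% at n = 12, so the stated minimum of 12 reproduces.

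**2. Patients behind each Cohort 2 mean** (6 per sequence; times from Figure 1):

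| Time (h) | 0.5 | 1 | 2 | 3 | 4 | 12 | 24 | 120 |
|---|---|---|---|---|---|---|---|---|
| Sequences | B | A | B, C | A, C | B | A, C | B, C | A |
| Patients | 6 | 6 | 12 | 12 | 6 | 12 | 12 | 6 |

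The Introduction puts the adult peak at 3 to 4 h. An averaged Cmax therefore rests on 12 of 18 patients (33% unused) or 6 of 18 (67% unused).

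**3. What those counts mean for the protocol's target.** The interval is exp(± t × 0.429/√n). It covers between-patient variation only and applies the AUC CV to Cmax, which is an assumption.

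| n | t × 0.429/√n | 90% CI relative to geometric mean | Power for 60–140% |
|---|---|---|---|
| 18 | 1.740 × 0.429/4.243 = 0.176 | 0.84–1.19 | 93.8% |
| 12 | 1.796 × 0.429/3.464 = 0.222 | 0.80–1.25 | 80.3% |
| 6 | 2.015 × 0.429/2.449 = 0.353 | 0.70–1.42 | 36.1% |

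**4. Simulated size of the loss.** The maximum of the means switches between 3 h and 4 h, so its variance should lie between the count ratios 18/12 = 1.5 and 18/6 = 3. Cohort 2 was simulated with a two-compartment oral model, 1,500 trials per setting. The 45% exposure CV is the protocol's. The rest is assumed: peak about 3.6 h, half-lives 3 h and 20 h, absorption-rate and lag CV 30–70%, residual error 15%.

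- Cmax CV, averaged profile against the mean of 18 true individual values: 14.5% v 10.7%, 14.9% v 11.1%, 16.2% v 12.0%. Variance ratios: (14.5/10.7)² = 1.84, (14.9/11.1)² = 1.80, (16.2/12.0)² = 1.82. Other absorption and lag values gave about 1.6 to 1.9.
- Cmax bias: 8.3%, 6.3% and 4.0% upward, because the largest of several noisy means is selected.
- AUC(0–24) CV: 11.5% v 10.5%, 11.7% v 10.4%, 12.2% v 10.7%. Variance ratios 1.20, 1.27 and 1.30.

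The comparator is ideal. A POP PK fit does not know the true individual values. For an assumed model with peak at 3.6 h, absorption-rate log SD 0.3 and residual log SD 0.1 to 0.2, its standard error for log Cmax is 0.105 to 0.112, against 0.429/√18 = 0.101 for the ideal. That is 8 to 23% more variance. Larger residual error raises the ratio to the ideal (about 2.4 at 0.3 on the log scale) but also worsens any fitted model.

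**5. What one profile can report.** SAP 6.1 asks for mean, median, SD, minimum, maximum and 95% CI. The synopsis asks for geometric mean and 90% CI by gender. One composite profile supplies one Cmax and one AUC, so SD and range do not exist. A CI would need a method for repeated samples within patients, and none is given. The alternative reading, averaging 18 individual values, is the one SAP 6.5.1 itself rejects.

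**6. Weight.** The Introduction predicts 60–88% relative exposure over male weights 67.3 to 40.7 kg, an implied exponent of magnitude ln(88/60)/ln(67.3/40.7) = 0.76. With 18 perfectly known exposures, its SE = √(0.429² − 0.76²s²)/(s√17), where s is the log-weight SD (assumed). At s = 0.15, 0.25 and 0.30 the SE is 0.67, 0.37 and 0.29.

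**The case against.** **Averaging is not the SAP's invention.** A reader might infer that the SAP overrode a clear protocol. The documents do not support that. The synopsis and SAP 4.1 allow average profiles, and the Amendment 2 rationale speaks both of combining sparse samples into an average time course and of POP PK modelling. Protocol 8.1, under its POP PK wording, defines AUC by the trapezoidal rule and Cmax as an observed maximum. This stands: part of the conflict is inherited. It does not define the average or remove the contradiction with SAP 3.1.

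**The protocol prescribes no particular model.** An adult model as starting structure and weight as a covariate are not specified for this analysis. That stands, so they can only be suggestions.

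**Development has stopped.** SAP 6.5.2 uses this reason to drop the other parameters, but SAP 6.5.1 does not use it for the primary ones. The primary objective is retained, and SAP 3.1 still says Part 1 data will determine the next age group's dose.

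**Weight.** A reader might infer that the weight question has become unanswerable. It has not: concentrations and weights are collected and could be modelled later. It is an aim in the Introduction and not a listed objective, and step 6 shows that even an ideal analysis would be imprecise. Nor should the spread in dose per kilogram at 80 mg (80/40.7 = 1.97 against 80/67.3 = 1.19 mg/kg, 1.65-fold) be read as exposure. The Introduction's predicted exposure spread is 88/60 = 1.47-fold in males and 74/60 = 1.23-fold in females.

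**Information lost.** A reader might infer that about half the information on Cmax is wasted. No single figure is supported. The count gives 33% or 67% depending on the peak time, and the simulated ratio is against an ideal. A 3 h mean still meets the protocol's minimum of 12.

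**Conclusion.** The point holds as an undeclared and undefined change in how the primary parameters are estimated for 18 of 21 patients, partly inherited from loose protocol wording. It is more than missing detail: SAP 6.5.1 promises summary statistics that a single pooled profile cannot produce.

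The part of the size that rests on the documents is the patient count at the peak, 12 or 6 instead of 18. Against the protocol's own target this means 80.3% or 36.1% power instead of 93.8%, if the AUC CV applies to Cmax and residual error is ignored. Under assumed kinetics with about 15% residual error, Cmax variance is about 1.6 to 1.9 times the ideal, an upper bound on what POP PK could recover, with upward bias of about 4 to 8%.

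The loss for AUC is small, 1.2 to 1.3 times. That figure is for AUC(0–24) and omits the 120 h sample, so it is only a guide to the primary AUC(0-last). The weight-based dosing aim goes unanswered by the planned analysis.

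**What to change.** Reconcile SAP 3.1, 4.1, 6.5.1 and 6.11, in one of two ways.

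**Preferred.** Estimate Cohort 2 AUC(0-last) and Cmax by POP PK, as SAP 3.1 states, using all Part 1 concentrations at actual sampling times. Specify the structural model, software and handling of values below quantitation. Report between-patient variability and intervals. Treat body weight as an exploratory covariate, noting the likely imprecision at n = 18, and keep the averaged profile as a descriptive display. The cost is SAP text and a modest modelling task on 3 × 9 + 18 × 4 = 99 post-dose samples, with no new patients or blood draws. The downside is model dependence, and some parameters may have to be fixed or given priors.

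**Otherwise.** Declare the switch in SAP 6.11, remove POP PK and the dose-determination statement from SAP 3.1, and state that Part 1 does not test the POP PK model or weight-based dosing. Define the composite profile: arithmetic or geometric means, nominal or actual times, and the rule for the last quantifiable point. Give a CI that respects repeated samples within patients, such as a bootstrap of patients within sequence, and drop SD and range for Cohort 2 parameters. This costs wording and a short program.

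Either way, state the CI level, since SAP 6.1 says 95% and the synopsis 90%.
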